8.1 Sample Size Considerations

An overall sample size of approximately 50 patients (25 per treatment group) is considered sufficient to assess the primary endpoint of the best percentage change in tumour size following treatment with setanaxib when administered with pembrolizumab, versus placebo when administered with pembrolizumab, in patients with recurrent or metastatic SCCHN. With 25 patients per treatment group, using a 2-sided t-test, there will be 85% power to detect a 20% mean difference between the treatment groups in best percentage change in tumour size, with an estimated SD of 30% and a 2-sided alpha of 20%. To mitigate risks from a higher than expected number of patients discontinuing the study early or declining to have imaging or biopsies at Week 9, up to an additional 20 patients (making a maximum of 70 patients) may be randomised.

The key secondary endpoints of numbers of CAFs, CD8⁺ TILs, and regulatory T-cells in tumour tissue and gene expression analysis in tumour tissue will be used to determine proof of concept. With 25 patients per treatment group, there will be 90% power to detect a limit fold change (LFC) of more than 1.5 in gene sequencing endpoints measured in tumour tissue, assuming at least 20 patients have an evaluable Baseline and post-Baseline tissue sample.

For the key secondary endpoint of PFS, if the true hazard ratio for PFS is 0.5, approximately 38 progression events as defined by RECIST v1.1 will be required to have > 80% power to demonstrate a statistically significant difference in PFS with 2-sided p<0.2.

8.2 Randomisation

Randomisation will be performed via centralised interactive response technology (IRT). On Day 1, eligible patients will be assigned to setanaxib or placebo in a 1:1 ratio, stratified by HPV status. Each patient will receive a unique randomisation number when he/she is assigned treatment. Patients will be allocated to treatment according to the randomisation code.

8.3 Blinding

The investigator, the site personnel, the sponsor and their representatives involved in monitoring and conducting the study, and the patients will be blinded to treatment assignments.

The randomisation lists containing the true treatment assignment and kit lists containing the IMP kit assignments of patients will be maintained by ICON IRT system and ALMAC Clinical Services respectively. This information will not be accessible to any blinded project team members prior to the primary analysis, nor to the investigators or patients prior to updated analysis.

Additional details regarding the unblinding process can be found in the Data Blinding and Documentation Plan for further details.

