3.3 End of Study

A patient is considered to have completed the study if he/she has discontinued study treatment, completed all tumour assessments until RECIST v1.1-defined disease progression, and performed the EoT and Safety/Efficacy Follow-up Visits. The end of the study is defined as the date of the last visit or last procedure of the last patient in the study.

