Investigators and patients will continue to be blinded to randomised study treatment after initial unblinding of data for the primary analysis until the final database lock.

Safety and tolerability data will be regularly reviewed by an unblinded IDMC, with the first assessment after approximately 12 patients (6 per treatment group) have had the opportunity to complete at least 1 cycle of pembrolizumab +/- setanaxib. Safety data analyses will be descriptive only and will be described in the SAP and IDMC charter.

After approximately 12 patients (6 per treatment group) have completed their Baseline and post-treatment biopsy, initial gene expression and biomarker data in tumour tissue may be reviewed by the sponsor, who will remain masked to randomised treatment assignment. A second review may be performed, if required. Analyses will be descriptive only. Further details will be provided in the SAP.

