8.4 Database Lock

The data cut off for the updated analysis (or primary analysis if the updated analysis is not performed due to close proximity to the primary), will also be the final database lock, as long as there are no patients remaining on treatment at the time of the data cut off. If patients remain on treatment after this data cut off, then an interim lock will be used for the primary analysis and the final database lock will occur once all patients have completed study treatment or withdrawn from the study. An updated safety analysis will be performed if the final database lock occurs after the interim lock. Full details of the primary and updated analyses are given in Section 12.5.

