10.10 Adverse Events

10.10.1 Treatment-Emergent Adverse Events

A treatment-emergent adverse event (TEAE) is an AE that occurs, having been absent before the first dose of IMP, or having worsened in severity or seriousness after the first dose of IMP, up to and including 28 days after the date and time of last dose of IMP.

Any AEs that occur 28 days after the date of the last dose of IMP will be considered a post-treatment AE and will be listed only.

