12.5 Efficacy Analyses

The data cut-off for the primary analysis will occur approximately 15 weeks after completion of enrolment, when all patients are expected to have had at least 5 cycles of pembrolizumab, at least two post-treatment scans, and the opportunity for a post-treatment tumour biopsy. This analysis will include the primary endpoint of best percentage change in tumour size and all secondary endpoints (excluding Cox proportional hazards for PFS) will be analysed. Investigators and patients will continue to be blinded to randomised study treatment after initial unblinding of data for the primary analysis until the final database lock.

An updated analysis may be performed after approximately 38 progression events have been reported. This updated analysis will include only the secondary endpoints of PFS, and OS in addition to an updated waterfall plot for the primary endpoint of best percentage change in tumour size.

During ongoing review of the overall progression event count, if the predicted timing of the initial and updated analyses are expected to be close in proximity, one analysis may be performed.

Efficacy analyses will be conducted using the FAS. To understand the robustness of the results from important protocol deviations, the primary efficacy analyses will also be performed using the PPS.

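### SAP 8.3 and 12.5 give different end dates for the blind of investigators and patients, and the SAP 8.4 lock conditions leave out the 28-day Safety Follow-up

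*SAP*

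**What the plan says.** **End of the blind.** SAP 8.3 withholds the randomisation and kit lists from blinded team members until the primary analysis, "nor to the investigators or patients prior to updated analysis". SAP 12.5 keeps investigators and patients "blinded to randomised study treatment after initial unblinding of data for the primary analysis until the final database lock". Protocol 8.1 agrees: they stay blinded after "initial unblinding of data for the primary analysis until the final database lock". The statistical methods in the Protocol Summary repeat this.

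**Final lock.** Under SAP 8.4 the cut-off for the updated analysis (or for the primary analysis, if the updated one is not performed) is also the final lock "as long as there are no patients remaining on treatment at the time of the data cut off". Otherwise an interim lock is used and "the final database lock will occur once all patients have completed study treatment or withdrawn from the study". An updated safety analysis is planned only in that second case.

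**Safety window.** SAP 10.10.1 counts TEAEs "up to and including 28 days after the date and time of last dose of IMP". SAP 8.0 has AEs recorded to 28 days after treatment discontinuation, with a Safety Follow-up Visit 28 days after the last dose. Under Protocol 3.3 a patient has completed the study only when, among other things, he or she has "performed the EoT and Safety/Efficacy Follow-up Visits".

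**The concern.** There are two separate gaps.

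First, the SAP gives two dates for the same restriction. They coincide only if nobody is on treatment at the updated cut-off, and SAP 8.4 plans expressly for the other case. Between the two dates, late safety data still depend on investigator judgement. The investigator decides whether an AE is related to IMP (Protocol 7.2.2). After the EoT Visit only SAEs considered related to IMP have to be reported (Protocol 7.4). An investigator who knew the arm could therefore influence both how a late event is labelled and whether it is captured at all.

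Second, the lock conditions ask whether patients are off treatment, not whether their safety window has closed. A database locked on those terms could hold incomplete TEAE data for the patients who stopped last.

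**Working it through.** **1. When the updated analysis falls.** Inputs from SAP 8.1: hazard ratio 0.5, two-sided alpha 0.20, power above 80%, about 38 events; allocation 1:1 (SAP 8.2). The Schoenfeld formula gives

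d = 4(z₀.₉₀ + z₀.₈₀)² / (ln 0.5)² = 4(1.2816 + 0.8416)² / 0.4805 = 37.5, rounded up to 38.

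Power at 38 events is Φ(√38 × 0.6931/2 − 1.2816) = Φ(0.855) = 80.4%. The plan's figure reproduces.

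**2. Can patients still be on treatment then?** About 50 and at most 70 patients are randomised (SAP 8.1).

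- 50 − 38 = 12 event-free (24%)
- 70 − 38 = 32 event-free (46%)

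These are ceilings on patients still treated, because event-free patients include those already off treatment for toxicity or withdrawal. They do not bound the number inside the 28-day window, since a patient whose progression is among the 38 events may have stopped only recently. Protocol 3.2 expects about 8 of 25 setanaxib patients to be treated for 12 months or more. That is a planning expectation, not a count at this cut-off, but it shows that the case of patients remaining on treatment is realistic.

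**3. Does the planned duration include the follow-up?** The maximum of 114 weeks (SAP 8.0) reproduces as 35/7 + 105 + 28/7 = 5 + 105 + 4 = 114. Treatment ends at week 5 + 105 = 110 from the start of screening. A lock on the literal wording of 8.4 could therefore come up to 4 weeks before the last patient's window closes.

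**4. The two 8.4 conditions against the TEAE window.** For a patient who took the last dose s days before the lock cut-off, with s below 28, 28 − s days of the window are missing.

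| Last dose before cut-off | Days missing of 28 |
|---|---|
| 7 days | 21 |
| 14 days | 14 |
| 27 days | 1 |

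- *First condition (the cut-off is the final lock).* The loss follows directly for anyone with s below 28. SAP 8.4 plans no later safety update here. SAP 6.0 foresees a small set of safety listings for patients continuing in the study after the updated analysis, which could include someone in follow-up. Those listings would have to come from a database that 8.4 treats as finally locked, and SAP 6.0 says the full outputs are not reproduced.
- *Second condition (later final lock).* The lock follows the end of treatment in all patients, with no stated interval. A lock soon afterwards would truncate windows; a lock after the last Safety Follow-up Visit would not. The text allows either.

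**5. The two blinding dates.** If nobody is on treatment at the updated cut-off, 8.3 and 12.5 name the same date. If someone is, 8.3 ends the restriction at the updated analysis and 12.5 at the later lock. The updated analysis is also optional (SAP 12.5), and if it is not performed the 8.3 limit has no defined date.

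**The case against.** A reader might infer that the SAP orders unblinding at the updated analysis, so that late safety data will be judged unblinded. The documents do not support that. SAP 8.3 sets an earliest date for access, not an instruction to release the code, and its opening sentence says investigators and patients will be blinded. SAP 12.5 and two places in the protocol say the opposite of the loose phrase, and 8.4 sends the reader to 12.5 for details. The unblinding process is deferred to a Data Blinding and Documentation Plan that is not among the documents. All of this stands, and it makes the point an inconsistency rather than a planned loss of blinding. It does not remove the inconsistency, because staff could follow either date and claim to comply with the SAP.

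A reader might also infer that the last patient will have none of the 28 days in the database. Under the second condition that is not certain. Completion of treatment by all patients is a precondition, not a same-day lock. The 28-day visit and AE recording remain mandatory, and Protocol 8.4.7 places the final PK analysis at the end of the study after database lock. The objection holds for that condition but not for the first, where the cut-off itself is the lock.

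Nor can it be said that the SAP fails to list a departure from its governing protocol. The SAP was written against protocol v5.0, and the protocol supplied is v4.0. The conflict between 8.3 and 12.5 lies within the SAP and does not depend on the version.

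**Conclusion.** The point holds as two wording defects. SAP 8.3 contradicts SAP 12.5 and the supplied protocol on how long investigators and patients stay blinded. This has a consequence only if patients are on treatment or in safety follow-up at the updated analysis and 8.3 is followed. SAP 8.4 omits the 28-day Safety Follow-up from both lock conditions. Truncation is clear where the cut-off is the final lock and a patient stopped IMP less than 28 days before; it is possible but not certain under the later lock.

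The effect is limited to descriptive safety data: relatedness, related-only late SAEs and completeness of TEAEs. The primary endpoint and the PFS comparison rest on cut-offs that precede any such unblinding. The number of patients affected cannot be derived. The range of 12 of 50 to 32 of 70 assumes exactly 38 events and that treatment stops at progression, and it is only a ceiling on patients still treated. The correction is worth making because it is specific and cheap.

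**What to change.** - **SAP 8.3:** change the limit for investigators and patients from the updated analysis to the final database lock, in line with 12.5, and check that the Data Blinding and Documentation Plan gives the same date.
- **SAP 8.4, first condition:** let the cut-off be the final lock only if no patient is on treatment or still within the 28-day (+7 days) Safety Follow-up.
- **SAP 8.4, second condition:** otherwise set the final lock after all patients have completed the Safety Follow-up Visit or withdrawn from the study.
- **Tidying:** 8.4 assigns the interim lock to the primary analysis in a sentence about the updated cut-off; say which is meant. Align the SAP 6.0 condition for addendum listings (patients continuing in the study) with the 8.4 condition (patients on treatment).

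The cost is SAP wording and a final lock later by up to 28 + 7 = 35 days, about 5 weeks. No additional data need to be collected, because the visit and the AE recording are already required.

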8.4 Database Lock

The data cut off for the updated analysis (or primary analysis if the updated analysis is not performed due to close proximity to the primary), will also be the final database lock, as long as there are no patients remaining on treatment at the time of the data cut off. If patients remain on treatment after this data cut off, then an interim lock will be used for the primary analysis and the final database lock will occur once all patients have completed study treatment or withdrawn from the study. An updated safety analysis will be performed if the final database lock occurs after the interim lock. Full details of the primary and updated analyses are given in Section 12.5.

9.0 Study Estimands

An estimand is a precise description of the treatment effect reflecting the clinical question posed by a given clinical trial objective. The estimand consists of five attributes: the treatment, the population, the variable, the specification of intercurrent events and how to account for these, and the population level summary.

9.1 Estimand Attributes

9.1.1 Primary Estimands

Primary Objective	Primary Estimand Attributes	
• To compare the change in tumour size per RECIST v1.1 in recurrent or metastatic SCCHN patients treated with setanaxib and pembrolizumab versus patients treated with placebo and pembrolizumab	 Treatment: setanaxib + pembrolizumab versus placebo + pembrolizumab. Population: Patients in the FAS who also have measurable disease at baseline. 	
	Variable:	
	Best percentage change in tumour size defined as the percentage change from Baseline in the sum of diameters of target lesions, as assessed by RECIST v1.1.	

Intercurrent Events:
1. Premature study discontinuation
2. Use of certain alternative or additional therapy including a new anti- cancer therapy
3. Premature study drug discontinuation/interruption
4. PD or Death
• Strategy: Hybrid (While on Treatment / Treatment Policy / Hypothetical)
A While on Treatment approach will address the first 2 intercurrent events listed above. Any values for the variable of interest after the occurrence of either of the first 2 intercurrent events listed are considered irrelevant in defining the treatment effect of interest, i.e. only values prior to the occurrence of the intercurrent event are considered.
A Treatment Policy approach will be taken where a patient prematurely discontinues treatment, i.e. all data will be used up to the point of PD.
A hypothetical approach will be taken where a patient has no evaluable post-baseline assessments, as a result of PD or death, by performing imputation (See Section 10.7.6).
Population Level Summary Measure:
The LS Mean difference (or geometric mean ratio if a log transformation has been applied), 80% CI and associated p-value for the treatment comparison will be obtained from the ANCOVA model.

9.1.2 Secondary Estimands

The attributes of the secondary estimands are the same as described for the primary estimand in Section 9.1.1 unless otherwise specified in the secondary attributes list below;

Key Secondary Objectives	Secondary Estimand Attributes
 To compare the PFS per RECIST v1.1 in recurrent or metastatic SCCHN patients treated with setanaxib and pembrolizumab versus patients treated with placebo and pembrolizumab 	 Variable: Time from randomisation to the first documented disease progression per RECIST v1.1 or death due to any cause, whichever occurs first. Intercurrent Events: Lacking disease evaluation. Premature study discontinuation Use of certain alternative or additional therapy including a new anti-cancer therapy Strategy: Hypothetical A hypothetical strategy will be applied using censoring rules (see Section 10.8.1). Population Level Summary Measure:
	The HR of PFS between the competing treatment groups.
 To compare the change from Baseline in CAFs level in tumour tissue from recurrent or 	• Variable:

metastatic SCCHN patients treated with setanaxib and pembrolizumab versus patients treated with placebo and pembrolizumab			Change from Baseline in CAFs level in tumour tissue.
			Strategy: Treatment Policy
			A Treatment Policy strategy will address the intercurrent events listed, by considering the intercurrent events irrelevant in defining the treatment effect of interest. The value for the variable of interest is used regardless of whether or not the intercurrent events occur.
• T n tu S p	To compare the change from Baseline in the number of CD8 ⁺ TILs and regulatory T-cells in tumour tissue from recurrent or metastatic SCCHN patients treated with setanaxib and pembrolizumab versus patients treated with placebo and pembrolizumab	•	Variables:
			CD8 ⁺ : Change from Baseline in CD8 ⁺ TILs numbers in tumour tissue.
			T-Cells: Change from Baseline in FOXP3 values.
		•	Strategy: Treatment Policy
			As described for CAFs level above.

Other Secondary Objectives	Other Secondary Estimands
 To assess the ORR, the DoR and DCR per RECIST v1.1 in recurrent or metastatic SCCHN patients treated with setanaxib and pembrolizumab versus patients treated with placebo and pembrolizumab 	 Variables: ORR: Proportion of the patients who have a CR or PR per RECIST v1.1. DCR: Proportion of the patients in whom the best overall response is determined as CR, PR, or SD per RECIST v1.1. Intercurrent Events: Premature study discontinuation Use of certain alternative or additional therapy including a new anti-cancer therapy PD or Death Premature study drug discontinuation/interruption
	 Strategy: Hybrid (While on Treatment / Treatment Policy) A While on Treatment approach will be taken to address the first 3 intercurrent events. Any values for the variable of interest after the occurrence of the intercurrent events listed are considered irrelevant in defining the treatment effect of interest, i.e. only values prior to the occurrence of the intercurrent event are considered. A Treatment Policy approach will be taken where patients prematurely discontinue/interrupt study treatment. The value for the variable of interest is used regardless of whether or not the intercurrent event occurs. Population Level Summary Measure: ORR and DCR: The summary measure of associated 90% Agresti-Coull confidence interval of ORR and DCR at each treatment group.
	 Variable: DoR: The minimum time when CR or PR is first observed to the time of PD or death. Intercurrent Events: Premature study discontinuation Use of certain alternative or additional therapy including a new anti-cancer therapy Premature study drug discontinuation/interruption Strategy: Hypothetical A hypothetical strategy will be applied using censoring rules (see Section 10.9.4). Population Level Summary Measure: DoR: Kaplan Meier estimates of the median and quartiles along with their 90% CIs using the Brookmeyer-Crowley method.

•	To assess the OS in recurrent or metastatic SCCHN patients treated with setanaxib and pembrolizumab versus patients treated with placebo and pembrolizumab	Note: 1 betwee Varia Time Intero 1. S Strato A Tre exper data o regari A hyp Secti Secti Vaplan 90% C	The secondary endpoint of OS will not be formally compared on the treatment groups. ble: from randomisation to death due to any cause. current Events: tudy completion / Data cut off egy: Hybrid of Treatment Policy and Hypothetical atment Policy approach will be taken where patients ience any intercurrent event other than study completion / cut off. The value for the variable of interest is used dless of whether or not the intercurrent event occurs. bothetical strategy will be applied using censoring rules (see on 10.8.2). Meier estimates of the median and quartiles along with their Is using the Brookmeyer-Crowley method.
•	To evaluate the safety and tolerability profile of setanaxib and pembrolizumab, versus placebo and pembrolizumab, in recurrent or metastatic SCCHN patients	This sa magnit estima	fety objective is not related to estimating or defining the ude of the treatment effect, hence the construction of an nd is not applicable.
•	To compare the change from Baseline in PD-L1 expression in tumour tissue from recurrent or metastatic SCCHN patients treated with setanaxib and pembrolizumab versus patients treated with placebo and pembrolizumab	 Varia Chan Strate As de 	ble: ge from Baseline levels of PD-L1 expression in tumour tissue. egy: Treatment Policy scribed for CAFs level above.
•	To compare the change from Baseline in patterns of gene expression and differential gene expression in tumour tissue from recurrent or metastatic SCCHN patients treated with setanaxib and pembrolizumab versus patients treated with placebo and pembrolizumab, using RNA sequencing	The bio magnit estima	omarker objective does not relate to estimating or defining the ude of the treatment effect, hence the construction of an nd is not applicable.
•	To assess the plasma exposure of setanaxib and its metabolite GKT138184	The Pł magnit estima	Cobjective does not relate to estimating or defining the ude of the treatment effect, hence the construction of an nd is not applicable.

